All data processing and analysis in the study will be conducted within the secure IT environment of the Clinical Informatics Research Group, at the University of Surrey. The information security policies and procedures of the Research Group have been approved by the NHS Digital as meeting Information Governance Toolkit (IGT) standards^{xii}.

The system is continuously being updated and modernized in respect of information processing, security and governance processes. The data are automatically extracted from the network of GP practices using a Simple Object Access Protocol (SOAP) web service, on a weekly basis. Data are uploaded to a secure Microsoft SQL server, and processed into aggregated tables; these are then linked to a pre-defined report structure using business intelligence software (Tableau Software, Inc. Seattle, WA, www.tableau.com), to produce a weekly surveillance report in a timely manner.

Using the EHR system, routine data as well as the content of encoded ADR cards will be extracted using methods that Surrey developed and deploys to extract RCGP RSC surveillance data. Sensitive coded data and free-text data will not be extracted. Only relevant EHR data for this study (e.g. disease or symptom, vaccination status and brand) coded by the GPs or other health professional will

¹ This is also referred to as “3DES”, which is the commonly used name for the triple data encryption algorithm (TDEA, also written Triple DEA) symmetric-key block cipher.

² RSA stands for Rivest, Shamir and Aldeman who founded RSA Laboratories. They created large numbers with only two prime factors, a core component of the encryption process

be extracted^{xiii}. Large volume of research that has come out of UK primary care is based on coded data^{xiv}. The quality of primary care data are such that the expectation will be able to detect frequent AEIs.^{xv}

GP practices will be required to use the relevant Read code for ADR notifications, when recording data from a returned card (Read Code: PPD - Adverse drug reaction notification).

Relevant coded data will be extracted, however these are limited to the administration regime, AEIs and batch number fields of prescribing data.

The following routinely collected patient data will be extracted for the study:

- Demographic information: age, gender, ethnicity, date of registration.
- Seasonal influenza vaccine information: date of administration, brand and batch number when available

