10	50000	5%	1785	17	1.00%	0.6%	1.5%	>99.99%	23.6%
11	50000	5%	1964	19	1.00%	0.6%	1.5%	>99.99%	22.5%
12	50000	5%	2142	21	1.00%	0.6%	1.5%	>99.99%	21.5%
13	50000	5%	2321	23	1.00%	0.6%	1.5%	>99.99%	20.7%
14	50000	5%	2500	25	1.00%	0.6%	1.5%	>99.99%	19.9%
1	50000	2%	71	0	1.00%	0.0%	5.1%	51.01%	118.1%
2	50000	2%	142	1	1.00%	0.0%	3.9%	76.00%	83.5%
3	50000	2%	214	2	1.00%	0.1%	3.3%	88.36%	68.0%
4	50000	2%	285	2	1.00%	0.1%	2.5%	94.30%	58.9%
5	50000	2%	357	3	1.00%	0.2%	2.4%	97.23%	52.7%
6	50000	2%	428	4	1.00%	0.3%	2.4%	98.65%	48.1%
7	50000	2%	500	5	1.00%	0.3%	2.3%	99.34%	44.5%
8	50000	2%	571	5	1.00%	0.3%	2.0%	99.68%	41.6%
9	50000	2%	642	6	1.00%	0.3%	2.0%	99.84%	39.3%

Week	Expected Population medically followed by the enrolled practices	Cumulative Vaccine coverage after 14 weeks	Cumulative number of Vaccinated subjects	Cumulative number of Subjects reported ≥ 1 AEI	Average Proportion of AEI reported	Lower 95%CL	Upper 95%CL	Cumulative Probability to observe at least one event	Associated Relative standard error (RSE)
10	50000	2%	714	7	1.00%	0.4%	2.0%	99.92%	37.2%
11	50000	2%	785	7	1.00%	0.4%	1.8%	99.96%	35.5%
12	50000	2%	857	8	1.00%	0.4%	1.8%	99.98%	34.0%
13	50000	2%	928	9	1.00%	0.4%	1.8%	99.99%	32.7%
14	50000	2%	1000	10	1.00%	0.5%	1.8%	>99.99%	31.5%

Statistical analyses

All data processing and statistical analysis will be performed within the secure IT environment of the Clinical Informatics Research Group, at the University of Surrey. R and SAS Software will be used for the statistical analyses. Statistical analyses will be described in details in a statistical analysis plan, including the methodology to account for the clustering effect.

Coded data will be interpreted by the creation of ontologies allowing to map to case-definitions, where available. However, no in depth descriptions required for case definition will be used such as in clinical trials. Meaning will be inferred from brief clinical coded information.

Sequence of analysis

Interim analysis

Weekly safety report

Weekly safety reports will be generated in order to be able to detect and potentially report any safety concerns in near real time manner. Analyses will be performed overall and by vaccine brand (*Fluarix Tetra* vs. others).

The weekly incidence rates of AEIs within 7 days will be estimated as follows:

- The denominator will consist of the number of subjects vaccinated two weeks before the week of interest

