- The numerator will encompass all subjects from the denominator reporting the AEI within 7 days following vaccination with a seasonal influenza vaccine

Final analysis after end of the surveillance period

Analyses of demographics/baseline characteristics

Characteristics of the participating GP practices (Clinical Commissioning Group (i.e. the administrative health division used in England), North/South, Urban/Rural, IMD, number of registered subjects (rounded to the nearest 1000 to avoid the identification of the GP practices) will be tabulated.

Demographic characteristics will be summarized using descriptive statistics:

- Frequency tables will be generated for categorical variables such as gender
- Mean, median, standard deviation, maximum and minimum will be provided for continuous data such as age.

Analyses of the primary objective

All analyses will be carried out overall and by vaccine brand (*Fluarix Tetra* vs. others), by age strata (6 months to 5 years; 6 to 12 years; 13 to 17 years; \geq 18-65 years; $>$ 65 years) and UK CMO-specified risk groups status (at risk/not at risk).

The weekly incidence rates (per 100 subjects) of AEIs within 7 days will be estimated as follows:

- The denominator will consist of the number subjects vaccinated the week before the week of interest (so reaching up to 7 days of follow-up post vaccination during the week of interest) and having received an ADR card.
- The numerator will encompass all subjects from the denominator reporting the AEI within 7 days following vaccination with a seasonal influenza vaccine derived from the ADR card

The cumulative incidence rates (per 100 subjects) of AEIs within 7 days will be estimated as follows:

- The denominator will be the number of subjects vaccinated at any point from study start up to the week before the week of interest (i.e. cumulatively since the beginning of the study) and having received an ADR card.
- The numerator will encompass all subjects from the denominator reporting the AEI within 7 days following vaccination with a seasonal influenza vaccine derived from the ADR card

95% confidence interval (CI) will be computed on the estimated incidence rates.

Analyses of the secondary objective

All analyses will be carried out overall and by vaccine brand (*Fluarix Tetra* vs. others), by age strata (6 months to 5 years; 6 to 12 years; 13 to 17 years; \geq 18-65 years; $>$ 65 years) and UK CMO-specified risk groups status (at risk/not at risk).

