9. CONDUCT OF ANALYSES

9.1. Sequence of analyses

Interim weekly safety reports and a final analysis after study end will be done.

Description	Analysis ID	Disclosure Purpose	Dry run review needed (Y/N)	Study Headline Summary (SHS) requiring expedited communication to upper management (Yes/No)	Reference for TFL
Final analysis after study end	E1_01	Study report, CTRS	No	Yes	Refer to EPI-FLU-055 VS UK (207781) TFL .docx
Interim analyses	E1_02	Safety monitoring	No	No	Weekly safety reports of EPI-FLU-046

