9.1.1. Interim analyses

Weekly safety reports of influenza vaccination and uptake by different age and risk groups and the EMA listed AEIs reported by the vaccinated subjects will be generated during the study period. These analyses will be performed overall and by vaccine brand (*Fluarix Tetra* vs. others).

The weekly incidence rates of each AEI within 7 days will be estimated as follows:

- The denominator will be the number of subjects vaccinated with a seasonal influenza vaccine during the week of interest
- The numerator will be the number of subjects from the denominator reporting the AEI within 7 days following vaccination with a seasonal influenza vaccine using data entered in the EHR

A safety report will be generated for each ISO week 35 to 48.

The safety report of a specific ISO week will be provided 3 weeks after that week to allow for data to be encoded in EHR.

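### The in-season weekly safety reports specify only a one-week, all-ages AEI rate, so a rise confined to one age group would be diluted

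*Protocol*

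**What the plan says.** **In season.** Under Weekly safety report, protocol section 5a gives the reports the task of detecting safety concerns in near real time, then states: "Analyses will be performed overall and by vaccine brand". The one estimator that follows uses subjects vaccinated in a single week. SAP 9.1.1 has the same structure. Its opening sentence describes "Weekly safety reports of influenza vaccination and uptake by different age and risk groups and the EMA listed AEIs reported by the vaccinated subjects", then adds "These analyses will be performed overall and by vaccine brand", and its only AEI denominator reads "The denominator will be the number of subjects vaccinated with a seasonal influenza vaccine during the week of interest". On timing it says "The safety report of a specific ISO week will be provided 3 weeks after that week". Neither section defines a cumulative AEI rate or an AEI rate by age.

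**After the season.** Cumulative denominators and AEI rates by age and risk status appear in the protocol under "Final analysis after end of the surveillance period". In the SAP they appear in sections 7.3.2 and 7.3.3, within section 7, which by its title covers the analysis after study completion.

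**Text that points wider.** The synopsis (Study design) speaks generally of weekly and cumulative analysis. The objectives and endpoints (protocol section 4b) name weekly and cumulative rates by age without tying them to the final report. SAP 9.1 gives "Weekly safety reports of EPI-FLU-046" as the layout reference for the interim analyses. The protocol's data management text says of the aggregated tables that "these are then linked to a pre-defined report structure". Neither that layout nor that structure is in the documents.

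**The concern.** The protocol's rationale (section 4a) wants a rise in reactogenicity found in near real time, in the earliest vaccinated cohorts. The weekly report is the instrument for that. If a rise is confined to young children, the written rule mixes them with every other age and starts afresh each week. The rows that would show the rise are required only after the study has ended, when they can no longer prompt action in that season.

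The brand split serves the product- and batch-specific aim but replaces an age split only in part. Children aged two to eight are due the live nasal vaccine while the practices mainly use the sponsor's vaccine, so a child signal would lean towards the non-GSK group. That group also contains adults.

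**Working it through.** **1. The plan's own precision figures.** Protocol Table 2, AEI probability 1%, 10% coverage:
- Week 1, n = 357: chance of at least one AEI = 1 − 0.99^357 = 97.23%; RSE = √(0.99/3.57) = 52.7%; exact 95% CI for 3/357 = 0.17% to 2.44%.
- Week 14, n = 5,000: RSE = √(0.99/50) = 14.1%; exact CI for 50/5,000 = 0.74% to 1.32%.

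These match the table. The fall from 52.7% to 14.1% comes from cumulating. A single-week rate on 357 vaccinees stays at 52.7% all season.

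**2. Inputs for the illustration.** From Table 2 at 10% coverage: 357 vaccinees a week, 2,500 by week 7. Assumed, because the documents give no values: all-ages AEI rate 5%; child rate (6 months to 5 years) 10% doubling to 20% from week 1; child share 2, 5 or 10%; no clustering.

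**3. Dilution.** New all-ages rate = 5% + share × (20% − 10%) = 5.2, 5.5 or 6.0%.

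**4. Chance of a visible rise.** The measure is the chance that the exact (Clopper-Pearson) lower 95% limit exceeds the old rate. Find the smallest count r that achieves this, then P(X ≥ r) under the new rate.

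| Rate shown | n at share 2 / 5 / 10% | r | Chance |
|---|---|---|---|
| One week, all ages (written rule) | 357 | 27 | 3 / 6 / 13% |
| One week, child row | 7 / 18 / 36 | 4 / 6 / 8 | 3 / 13 / 43% |
| Cumulative to week 7, all ages | 2,500 | 148 | 6 / 19 / 58% |
| Cumulative to week 7, child row | 50 / 125 / 250 | 10 / 20 / 36 | 56 / 89 / 99% |

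Neither splitting by age alone nor cumulating alone is enough; most of the gain comes from doing both.

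**5. Allowing for repeated looks.** At least one crossing in the first seven reports:
- Weekly all-ages rate, 1 − (1 − q)^7 with q = 0.035, 0.061, 0.130: 22 / 35 / 62%. With no rise, q = 0.023 gives 15%.
- Cumulative child row (simulation, 100,000 runs): 63 / 92 / 99%. With no rise, 5 / 6 / 7%.

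**6. Does the brand row stand in for age?** Take a 5% child share, with all 18 children of the week in the non-GSK group. By week 7 the non-child rate is (125 − 12.5)/2,375 = 4.74%. If non-GSK vaccines are 50, 20 or 10% of vaccinees (n = 178, 71, 36), the group rate moves from 5.3% to 6.3%, 6.1% to 8.6%, or 7.4% to 12.4%. One week crosses with chance 6 / 8 / 15%.

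**7. Less favourable inputs, cumulative child row at week 7.**
- Child rate 5% to 10%: 23 / 60 / 83%.
- Child rate 1% to 2%: 8 / 11 / 24%.
- 10% to 20% with design effect 2 (effective n about 25, 62, 125): 22 / 60 / 89%.
- 5% to 10% with design effect 2: 10 / 28 / 60%.

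**The case against.** **The text may mean more than it says.** In SAP 9.1.1 the analyses split by brand could be taken to include the outputs by age just named. The synopsis puts brand, age and risk status in one list ahead of AEI reports. The objectives ask for age-specific cumulative rates, and the prior-season layout may show them. This stands as a limit: the gap is in the written rule and does not prove that the reports lacked these rows. The narrower reading remains likelier, because the estimator itself names no age, and the synopsis promises that AEIs will be listed, which is not a rate.

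**Readers can add up the weeks.** Weekly cohorts do not overlap, so overall and by-brand cumulative rates can be summed from successive reports if counts are shown. That is fair, but age rows cannot be recovered this way, and the summed all-ages rate reaches only 6 / 19 / 58%.

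**The example is favourable.** It compares seven weeks with one, and its inputs are assumed. The seven-report comparison in step 5 narrows the gap without closing it. For rare events, low child shares or strong clustering the gain is modest. Children aged 4-5 are moving to school vaccination, which makes low shares plausible.

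**No decision rule is affected.** All analyses are descriptive, so the crossing measure is only a yardstick. Serious events that the university team learns of and that are deemed related to a GSK flu vaccine go to the sponsor within 24 hours by a separate route. That is true, but the study also aims to detect more frequent expected reactions, and these depend on the rates.

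**Conclusion.** The concern holds as a statement about the written rule. Protocol section 5a and SAP 9.1.1 require one single-week AEI rate, overall and by brand; cumulative and age-specific AEI rates are required only for the final analysis. The dilution is arithmetic: a doubling in children from 10% to 20% moves the all-ages rate from 5% to no more than 6.0% for child shares up to 10%. The detection chances rest on assumed rates, shares, even weekly vaccination and, in the main case, no clustering. They shrink markedly at low AEI rates, but the cumulative age row comes out ahead of the pooled rates in the main case. The plan should be changed. Confidence is medium, because the prior-season layout and the pre-defined report structure could not be seen.

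**What to change.** In the protocol's Weekly safety report section, and to match in SAP 9.1.1, state that each report also gives any AEI and each of the nine AEI categories by the five EMA age groups: numerator and denominator for the week, plus the cumulative rate since 1 September with its 95% CI, overall and, where numbers allow, by brand. Keep the weekly overall and by-brand rates. Say that the age rows are read descriptively. If the EPI-FLU-046 layout already has these rows, one sentence saying so is enough.

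The cost is wording and interim report programming. Age is already extracted, and the same tables are needed for SAP 7.3.2 and 7.3.3. The downsides:
- **Sparse rows** for children.
- **Chance crossings.** 10 outcomes × 5 ages = 50 cumulative rates per report, so up to 50 × 0.025 = 1.25 by chance (150 rates and 3.75 with two brand groups). One child row with no rise crosses at least once in 14 looks in 7-9% of simulations.
- **Slow response to late rises.** If the all-ages rate doubles from 5% to 10% in week 11, that week's rate crosses with chance 95%, but the cumulative rate (n = 3,927 at 5.45%) with 23%. A child rise from week 8 at 5% share gives the cumulative child row 5% at week 8, 22% at week 10 and 63% at week 14. This is why the weekly rates must stay.

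On timing, the SAP is dated 11 December 2017. With the three-week lag, the week 46 report fell due on 10 December (19 November + 21 days), so 12 of 14 reports were already due. The protocol is where the change would have acted in season.

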7. ETHICAL CONSIDERATIONS

The primary purpose of this study is to work with practitioners, governance experts, and a commercial MAH to develop robust process for the annual enhanced safety surveillance of seasonal influenza vaccines recommended by the EMA.

The principal ethical issue is concerned with the protection and use of anonymised patient level information for the purpose of surveillance of safety of seasonal influenza vaccination as recommended by the EMA. NHS guidelines specify that a Section 251 approval is required when conducting research using anonymised patient level data, without individual level patient consent; approval is also dependent on the requesting institution meeting specific requirements of information governance, which the University of Surrey secure network exceeds. The protection and use of anonymised patient level information is addressed more fully in the next section: information governance considerations.

The University of Surrey team will seek approval from the University Ethics Review Committee. In addition, the formal opinion of the Proportional Review System of the National Ethics Review Service will be sought regarding the need for NHS Research Ethics Committee (REC) approval.

'Defining Research' (<http://www.hra.nhs.uk/documents/2013/09/defining-research.pdf>), the National Research Ethics Service (NRES) guidance suggests that surveillance does not require formal review by a Research Ethics Committee. The research team will however seek an opinion from the NRES's Proportional Review system to check if formal approval from a NHS Research Ethics Committee (REC) is needed prior to the commencement of the study, as well as Section 251 approval^{xx}. If the proportional review suggests that a full NHS REC review is necessary, then applications will be submitted to the REC as well as the Clinical Research Network (CRN) and, if advised, the Confidential Advisory Group (CAG) for formal approval for Section 251 of NHS Act 2006 and Health Service (Control of Patient Information) Regulations 2002 exemptions.

Section 251 of the Health and Social Care Act 2001, allowed the Secretary of State to set aside the common law duty of confidentiality for defined medical purposes. Surveillance is generally taken to be one of the defined medical purposes for which data can be used. As it has not been tested whether the Health and Social Care Act is retrospective data are generally not extracted for periods prior to that Act, without a clear need generally approved by an ethics committee.

This study is piloting enhanced passive surveillance as recommended by EMA. Such surveillance is not expected to require taking active consent. Generally, collecting surveillance data in an anonymised form is lawful, acceptable as use of data for public health purposes is recognised to be in the public interest. Based on our experience with the EPI-FLU-045 & EPI-FLU-046 pilot studies, the expectation is that this investigation meets the Health Research Authority's definition of Service Evaluation^{xxi}. The expectation is that the current enhanced passive surveillance (EPI-FLU-055 pilot studies) falls under the same criteria^{xxi}.

8. INFORMATION GOVERNANCE CONSIDERATIONS

The Clinical Informatics Research Group at the University of Surrey has worked with routinely collected healthcare data in a number of research and evaluation projects for over 15 years. The Research Group works within the research and Information Governance frameworks for health and social care in the United Kingdom, and is compliant with the University's best practice standards. The University of Surrey is registered with the Information Commissioner's Office Data Protection Register, and is compliant with the Data Protection Act, and other legislations.

In addition, the Research Group reviewed its departmental information governance policies and procedures, against the requirements of the NHS IGT for Hosted Secondary Use Team/ Project, Version 12^{xxii}. The review was approved by the Health and Social Care Information Centre, and was deemed satisfactory to support application to Confidentiality Advisory Group or the Data Access Advisory Group.

In line with the principle of the Data Protection Act 1998, data subjects will be informed of the uses of their data in this study. Participating GP practices will be asked to display project information in their website, and project information posters in reception areas, from when the practice has consented to take part in the study and until the study is completed.

The project information will specifically refer to the right of the patients to opt out if they do not wish their data to be included in this study. The codes in the data indicating that a patient does not wish to have their record available for research will be carefully considered. However, the number of patients within a practice who have chosen to opt out will be reported.

No Personally Identifiable Information (PII) such as NHS numbers, postcodes, dates of birth, etc. will be available to GSK, third parties, or disclosed in publications. Additionally, no patient level data will be sent to GSK to remove any possibility that any individual patient might be re-identified. GSK will also be blind to practice identities, and the locality at which any AEI occurs; other than where the patient gives consent, or their own chooses to report any condition in line with best practice.

9. DISSEMINATION AND PUBLIC REGISTER DISCLOSURE

The final agreed protocol of this study is intended be published in a peer review open access journal.

The outputs from the research will be disseminated primarily through peer review papers within the domains of primary care, surveillance, vaccines, and infectious diseases^{xxiii xxiv}. Findings will be presented at relevant seminars and conferences.

The University of Surrey, in accordance with GSK policy, will post a summary of the study protocol and subsequently results within 12 months of study completion and following review and comment by GSK on GSK's Clinical Study Register, accessible at <http://www.gsk-clinicalstudyregister.com> and at www.clinicaltrials.gov.

CONFIDENTIAL

207781 (EPI-FLU-055 VS UK)

Final Protocol

